12.0 Provisions to Monitor the Data to Ensure the Safety of Subjects*

This section is required when research involves more than Minimal Risk to subjects.

N/A

13.0 Withdrawal of Subjects*

13.1 Describe anticipated circumstances under which subjects will be withdrawn from the research without their consent.

We do not anticipate that individuals will be withdrawn without their consent.

13.2 Describe any procedures for orderly termination.

PROTOCOL TITLE: Comparing Program Options for Latinos with Diabetes

Participation for women who become pregnant during the study will be ended. They will be given an end-of-study visit where we will inform them that we are unable to continue their participation in the study and we will thank them for their participation. They will be told that their participation in the diabetes program they attend will not be affected by the fact that they have ended participation in the study.

13.3 Describe procedures that will be followed when subjects withdraw from the research, including partial withdrawal from procedures with continued data collection.

Participation for women who become pregnant during the study will be ended. They will be given an end-of-study visit where we will inform them that we are unable to continue their participation in the study and we will thank them for their participation. They will be told that their participation in the diabetes program they attend will not be affected by the fact that they have ended participation in the study.

Our Data Manager will create a separate project on REDCap to track individuals who have withdrawn themselves, been withdrawn due to pregnancy, or who have discontinued as a result of attrition.

Statistical methods using validated methods to handle missing data (MD-2, MD-3). As described above, all attempts to minimize missing data will be made. Despite these attempts, we realistically expect there to be some degree of missingness. Of particular interest is whether participants are missing any outcome data. We will determine whether it is missing completely at random (MCAR), missing at random (MAR), or missing not at random (MNAR). MCAR is defined as missingness that is independent of the observed and unobserved data (example: A1c measurement not obtained due to random machine failure); MAR is defined as missingness dependent only on an observed variable within the data (example: participant accidentally skips one question on the PAM-13); and MNAR is a systematic pattern to or a reason for the missingness (example: many participants exclude answering a question on the DKQ for a specific reason, either accidentally or intentionally). For MNAR, we will perform sensitivity analyses such as conducting the primary and secondary analyses on the intention-to-treat and per-protocol populations and compare the results. Under the assumption that most missing data is MAR or MCAR, we may use multiple imputation¹²⁶⁻¹²⁹ to create imputed data sets containing estimates from a random sample of missing values for each observation based on other non-missing covariates for each subject. Each imputed data set is then analyzed as described in the statistical analysis plans for the outcome measures, and the results from each analyzed data set are combined for statistical inference. Multiple

imputation will be performed using PROC MI and PROC MIANALYZE in SAS 9.4 or in Stata 13.1 or higher.

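### The missing-data plan makes its sensitivity analysis depend on a MAR-or-MNAR finding that observed data cannot supply, defines MNAR without reference to unseen values, and names a sensitivity analysis that does not test them

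*Combined protocol and SAP*

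**What the plan says.** The missing-data text closes section 13.3. It starts by classifying missing outcomes: "We will determine whether it is missing completely at random (MCAR), missing at random (MAR), or missing not at random (MNAR". It names no test, data source or decision rule for doing so. The three classes are then described:

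- MCAR: "MCAR is defined as missingness that is independent of the observed and unobserved data", illustrated by a machine failure.
- MAR: "MAR is defined as missingness dependent only on an observed variable within the data", illustrated by "example: participant accidentally skips one question on the PAM-13".
- MNAR: "MNAR is a systematic pattern to or a reason for the missingness", illustrated by the case where "many participants exclude answering a question on the DKQ for a specific reason, either accidentally or intentionally".

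Methods are attached to the classes. On one side: "For MNAR, we will perform sensitivity analyses such as conducting the primary and secondary analyses on the intention-to-treat and per-protocol populations", with the results compared. On the other, multiple imputation is optional and is introduced with "Under the assumption that most missing data is MAR or MCAR". Neither analysis population is defined.

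Three other places bear on this. Section 11.1 plans a REML linear mixed model for A1c, with BMI and depression scores handled in a similar way. For DKQ and PAM-13, the only model described is the multiple linear regression of 6-month change scores in section 11.2. Section 11.2 anticipates 20% attrition, and section 24.2 reports past retention of 80-85%.

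**The concern.** There are three linked faults.

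1. **The trigger.** MAR and MNAR differ only in how missingness relates to values nobody has seen. A step that promises to tell them apart cannot deliver, and the sensitivity analysis hangs on its result. If the team concludes MAR, nothing in section 13.3 obliges it to run one.
2. **The label.** Having a pattern or a reason is not what makes data MNAR. Missingness driven by site, visit or an earlier score has both and is still MAR, which imputation or a likelihood-based model can handle.
3. **The check itself.** Comparing two analysis populations does not ask what would happen if the unseen values were worse than predicted.

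At stake is how far the site comparison can be trusted when about one patient in five may be missing. The comparison is not randomised, and the two programs differ in structure, so dropout could differ by site. A regression on 6-month change scores leaves out anyone without a 6-month score unless values are imputed. Section 13.3 is therefore the only protection for the co-primary outcomes.

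**Working it through.** **Step 1. The plan's own figure.** Section 11.2 enrols 120 per site for 96 complete at 20% attrition: 96 / (1 - 0.20) = 120, and 120 x 0.80 = 96. Reproduced.

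**Step 2. The definitions applied to one case.** Take dropout that depends only on site and baseline score. Both are observed, so it meets the plan's MAR definition. It also has a pattern and a reason, so it meets the plan's MNAR definition. The two classes overlap. The MAR example does not illustrate its definition: an accidental skip is MCAR unless it is linked to an observed variable such as age or language. The MNAR example admits accidental omissions too.

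**Step 3. Can the data choose between MAR and MNAR?** Inputs from section 11.2 are a planned A1c difference of -0.5 (SD 1.0) and 20% missing. Assumptions: completers show -0.5, the missing fraction m is equal at both sites, and the unseen CCM values average k points worse than MAR predicts, with DSMS as predicted. Then

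full-sample difference = -0.5 + m x k

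| k (assumed) | m = 0.20 | m = 0.15 |
|---|---|---|
| 0 (MAR) | -0.50 | -0.50 |
| 0.5 | -0.50 + 0.10 = -0.40 | -0.50 + 0.075 = -0.425 |
| 1.0 | -0.50 + 0.20 = -0.30 | -0.50 + 0.15 = -0.35 |
| 2.5 | -0.50 + 0.50 = 0.00 | -0.50 + 0.375 = -0.125 |

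The 15% column uses the upper end of the retention range in section 24.2. Within a column, every row has the same observed data, so no test on those data can pick a row.

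**Step 4. The co-primary outcomes.** The same formula with an assumed departure of half the planned SD at one site and m = 0.20:

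- DKQ (planned 2.2, SD 3.8): 0.20 x 1.9 = 0.38, and 0.38 / 2.2 = 17%.
- PAM-13 (planned 12.7, SD 24.8): 0.20 x 12.4 = 2.48, and 2.48 / 12.7 = 20%.

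At m = 0.15 these become 0.285 (13%) and 1.86 (15%).

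**Step 5. Why the label matters.** This was simulated with 2,000 runs, 120 per site and a true difference of -0.50. The outcome was 0.6 x a standardised baseline plus noise with SD 0.8. The log-odds of being missing were -1.6 plus baseline at one site and -1.6 minus baseline at the other, which gave about 21% missing. All of this is assumed.

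- Missingness driven by site and baseline: the unadjusted complete-case estimate averaged -0.72, and the baseline-adjusted estimate -0.50.
- Missingness of the same form driven by the outcome itself: the same adjusted model averaged -0.70.

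The first case has a pattern and a reason, and adjustment cures it. The second is MNAR, and adjustment does not. The plan's MNAR definition does not separate them.

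**The case against.** The strongest reply is that the text is looser than a decision rule. Imputation is optional and rests on a stated assumption about most of the missing data, not on a test. Nothing says it is withdrawn once MNAR is suspected. Read in order, the MAR definition comes first and covers dropout explained by site or an earlier score, which leaves MNAR as the residual class. The MCAR and MAR definitions are essentially standard. The planned REML mixed model for A1c, with BMI and PHQ-9 handled similarly, already gives the secondary outcomes a likelihood-based analysis. Section 13.3 also records withdrawals, pregnancy exclusions and attrition in a separate project, which could raise suspicion of non-random dropout.

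Most of this stands, and it rules out several stronger inferences. A reader might infer that MAR data would necessarily be labelled MNAR, or that such data would be taken away from imputation. The overlap supports only that they could be mislabelled, and the text does not bar imputation. A reader might also infer that truly non-random dropout would never be flagged. It cannot be confirmed from observed data, but recorded reasons, together with so broad a definition, could still set off the check.

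The reply does not rescue the promise to determine the mechanism, the omission of unseen values from the MNAR definition, or the choice of sensitivity analysis. The mixed model itself relies on MAR, which the plan does not say.

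**Conclusion.** The point holds as a should-fix. A stated rule is wrong as written: the sensitivity analysis is conditional on something the data cannot show, the MNAR definition overlaps the MAR one, and the named check does not address unseen values. The exposure is greatest for DKQ and PAM-13.

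The shifts of 0.10 and 0.20 in A1c (0.075 and 0.15 at 15% missing), and those for DKQ and PAM-13, give scale only. They rest on assumed departures at one site, and 1.0 A1c point is a full planned SD. They should not be read as estimates of bias in this study. They would also exist under a correctly stated MAR analysis. What the present plan lacks is any analysis that would show them.

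**What to change.** Revise the missing-data paragraph of section 13.3 as follows:

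1. Remove the commitment to determine the mechanism.
2. Keep the MCAR and MAR definitions. Redefine MNAR as missingness that still depends on unobserved values given the observed data, and replace the MAR example with one tied to an observed variable.
3. State that the main analysis assumes MAR given site, baseline and all observed visit scores. Use a mixed model, or multiple imputation that includes those variables. Say explicitly which applies to DKQ and PAM-13.
4. In every case, run a prespecified sensitivity analysis that varies the unseen values by site, for example delta-adjusted imputation over a stated range. Any intention-to-treat versus per-protocol comparison would be additional, with both populations defined.
5. Report missingness by site and by earlier score.

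The cost is SAP wording and one extra analysis, with no change to data collection or sample size.

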Surveys. We will hire four individuals from the population of study to work as PDCSs. The PDCS at each site will administer a survey orally to all patient and social support participants at baseline (when they enter the study), with follow-up at 3, 6, and 12 months. The survey will consist of questions from or modified from four validated and reliable tools: 1.) The *Consumer Assessment of Healthcare Providers and Systems Cultural Competence Set (CAHPS-CC)*^{88,89} [as part of the programmatic assessment discussed in the preceding paragraph—will be administered at 3, 6 and 12 months only]; 2.) The *Diabetes Knowledge Questionnaire (DKQ)*^{51–53,112}; 3.) The *Patient Activation Measure (PAM-13)*^{55–62,113}; and 4.) The *Patient Health Questionnaire 9 (PHQ-9)*.^{70–73}

Interviews with patient and social support participants. We will conduct 72 interviews with patients and social supports (12/year x 2 sites x 3 years). Following Guest, Bunce and Johnson,¹¹² and [name]'s own experience with interview data, we believe that data sets of 12 interviews per site per year will capture a sufficient range of responses to achieve

PROTOCOL TITLE: Comparing Program Options for Latinos with Diabetes

thematic saturation. Our sampling frame for each set of 12 interviews will include six patients and six social supports. Interviews will be conducted with the social supports who correspond to the six patient interviewees. Interviews will follow the same format described in the programmatic assessment above. Spanish transcripts will be translated into English for analysis.

Focus groups. We will conduct 12 focus groups (2/year x 2 sites x 3 years). Focus group participants will be distinct from those recruited to participate in the interviews described in the preceding paragraph. Focus groups will include six distinct participants each (three patients and their corresponding social supports per focus group x 12 focus groups = 72 participants). The focus group questions and protocol will be an adaptation of that described above for the interviews.

Physical Measures. These measures will be obtained from patients at baseline with follow-up at 3, 6, and 12 months:

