We will create a database with all interview and focus group transcripts. We will conduct a theory-driven qualitative content analysis. We will read through transcripts to identify conceptual categories and patterns related to specified domains of inquiry, create a qualitative codebook, and develop conceptual summaries for each transcript. Following review and summary, we will code transcripts for systematic themes and sub-themes within the domains. We will explore interconnections between theme categories and develop a holistic interpretation of the data.

Statistical Analysis Aim 3. We will conduct analyses to assess successful patient management of their diabetes (Aim #3), our secondary outcomes, by measuring their A1c from blood samples drawn, BMI calculations, cortisol from hair samples, and PHQ-9 scores obtained at baseline, 3, 6, and 12 months. Clinical analysis of blood samples will use A1c tested on whole blood as described previously. Change in A1c over the four time points in each of the diabetes self-management program models will be evaluated by fitting a linear mixed model to A1c with the primary independent variable treatment site while adjusting for demographic covariates, social support and knowledge, the measures hair cortisol indicating stress levels, and participant and social support scores on the CAHPS-CC. An interaction between time and site will be included to explore how A1c scores change over time. For the secondary endpoint analysis, REML-adjusted least-squares mean estimates of change in A1c from baseline to 6 months post-intervention will be reported along with their 98.3% confidence intervals (the significance level includes a Bonferroni adjustment for three secondary outcomes). A model incorporating the 12 month time point will also be evaluated. BMI and depression scores will be analyzed similarly.

11.2 Provide a power analysis.

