- 1.) Hypothesis: The CCM model will result in a larger decrease in percent A1c from baseline to 6 months with Cohen's f ES = 0.06 as compared to the DSMS. Previously published studies and institutional experience evaluating culturally competent diabetes management programs report changes in percent A1c with effect sizes of 0.01 to 0.06 in studies ranging in sample size per arm from 26 to 133.^{66,105-107}
- 2.) Hypothesis: The CCM model will result in a larger decrease in BMI from baseline to 6 months than DSMS with a clinically meaningful difference of 1.5 kg/m² between the groups (Cohen's f ES = 0.06).^{67,68}
- 3.) Hypothesis: Compared to DSMS, CCM will result in a larger decrease (by 3 points) in PHQ-9 scores from baseline to 6 months (Cohen's f ES = 0.06).¹⁰⁷⁻¹⁰⁹

Note: It is coincidental that the effect sizes (and power) are the same for each of the three secondary outcomes

Power Calculations. We will recruit N=240 patient-social support pairs (n=120 per site) with anticipated 20% attrition to obtain complete data on at least n=96 per site. Comparing response changes on the DKQ, PAM-13, and DHQ-9 from baseline to 6 months between the CCM to the DSMS, the two-sided Type I error rate was adjusted for the number of comparisons made (four comparisons for the co-primary outcomes) using a Bonferroni correction ($\alpha=0.0125$). The power analyses for detecting site differences among change scores were based on multiple linear regression models including demographic characteristics, participants' perceived cultural competence of providers (CAHPS-CC), and social supports' change scores on the DHQ, PAM-13, and DHQ-9 as covariates. We report Cohen's f effect sizes based on the regression method.^{110,111}

The power for the primary endpoints with n=96 per site and $\alpha=0.025$ are as follows:

- 1.) Change in DKQ summed score: $\Delta_{CCM-DSCS} = 2.2$ (SD = 3.8), power = 96%, Cohen's f effect size (ES) = 0.09
- 2.) Change in PAM-13 raw score: $\Delta_{CCM-DSCS} = 12.7$ (SD = 24.8), power = 85%, Cohen's f ES = 0.07

The power for the secondary endpoints with n=96 per site and $\alpha=0.017$ for comparing the CCM to the DSMS:

- 1.) Change in A1c: $\Delta_{CCM-DSCS} = -0.5$ (SD = 1.0), power = 84%, Cohen's f ES=0.06.
- 2.) Change in BMI: $\Delta_{CCM-DSCS} = -1.5$ (SD = 3), power = 84%, Cohen's f ES=0.06.
- 3.) Change in depression scores (PHQ-9): $\Delta_{CCM-DSCS} = -3$ (SD = 6), power = 84% Cohen's f ES = 0.06.

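### The only check named for not-at-random missing data, intention-to-treat versus per-protocol, leaves the assumption about unseen outcomes unchanged and so cannot isolate or bound the bias

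*Combined protocol and SAP*

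**What the plan says.** The missing-data paragraph in section 13.3 expects some outcome data to be missing and begins by classifying the mechanism: "We will determine whether it is missing completely at random (MCAR), missing at random (MAR), or missing not at random (MNAR". For MNAR it offers "sensitivity analyses such as conducting the primary and secondary analyses on the intention-to-treat and per-protocol populations and compare the results". The wording leaves room for other analyses, but names none. For the rest it says: "Under the assumption that most missing data is MAR or MCAR", "we may use multiple imputation". Imputation is therefore optional, and it draws on each patient's observed covariates.

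For A1c, section 11.1 plans on "fitting a linear mixed model to A1c", with BMI and depression scores handled similarly. A likelihood-based mixed model also relies on MAR. For the primary outcomes, section 11.2 says only this: "The power analyses for detecting site differences among change scores were based on multiple linear regression models". That describes how power was calculated; the documents do not set out a primary analysis model for DKQ and PAM-13.

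Section 11.2 allows for "anticipated 20% attrition", from 120 to 96 patients per site. Section 9.2 schedules surveys at baseline, "with follow-up at 3, 6, and 12 months", so 3-month values will exist for many patients who lack a 6-month value. Intention-to-treat and per-protocol are not defined anywhere, and the plan does not say how patients without 6-month data enter the intention-to-treat set.

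**The concern.** MNAR means that, given everything observed, the chance of being missing still depends on the unseen value. A sensitivity analysis for it has to vary what is assumed about that value. Moving between two analysis populations does not: in each, the unseen outcomes are either left out or filled in from observed data.

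The trigger is a second problem. Observed data can speak against MCAR, but they cannot separate MAR from MNAR. An analysis that runs only once MNAR has been determined may never run, or may run on a judgement the data cannot support.

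The stake is the site comparison. Sites are not randomised and the programs differ in kind, so nothing makes the patients lost at one site depart from prediction in the same way as those lost at the other. As written, the plan would not show how far a reported difference depends on patients who were not seen.

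**Working it through.** **Inputs (section 11.2).** 120 enrolled per site, 20% attrition. Planned differences and SDs of change: DKQ 2.2 and 3.8; PAM-13 12.7 and 24.8; A1c -0.5 and 1.0; BMI -1.5 and 3; PHQ-9 -3 and 6. The section gives two alphas for the primary outcomes, 0.0125 in the text and 0.025 with the power figures, and 0.017 for the secondary outcomes. Both primary levels are used below.

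**The plan's own figures.** 120 × 0.80 = 96 per site reproduces. With 96 per site, two-sided noncentral t power is 95.9% for DKQ at 0.025 (stated 96%) and 85.4% for the secondary outcomes at 0.017 (stated 84%). PAM-13 gives 90.0% at 0.025 and 84.6% at 0.0125, against a stated 85%. The alpha conflict is a separate matter, but it is why two sets of results are shown.

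**Bias and type I error.** Assume 20% are missing per site at 6 months, no true difference, and dropouts at one site only worse than MAR predicts by a given shift.

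- Bias = 0.20 × shift, in SD units.
- Standard error = √(2/96) = 0.1443 SD.
- Noncentrality = bias / 0.1443; 190 degrees of freedom; critical t 2.259 (0.025), 2.522 (0.0125), 2.408 (0.017).

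| Shift at one site | Bias | Noncentrality | At 0.025 | At 0.0125 | At 0.017 |
|---|---|---|---|---|---|
| 0.25 SD | 0.05 SD | 0.346 | 3.4% | 1.8% | 2.4% |
| 0.50 SD | 0.10 SD | 0.693 | 6.2% | 3.6% | 4.6% |
| 1.00 SD (extreme) | 0.20 SD | 1.386 | 19.4% | 13.1% | 15.6% |

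Biases of 0.05 and 0.10 SD are 9% and 17% of the planned DKQ effect (0.579 SD), and 10% and 20% of the planned PAM-13 (0.512 SD) and A1c (0.5 SD) effects. With 15% missing (102 per site), shifts of 0.25 and 0.5 SD give 3.0% and 4.6% at 0.025.

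**Tipping points if the planned effect is observed.** Shift = (planned effect - critical t × 0.1443) / 0.20.

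- DKQ: (0.5789 - 0.3261)/0.20 = 1.26 SD at 0.025; (0.5789 - 0.3640)/0.20 = 1.07 SD at 0.0125.
- PAM-13: (0.5121 - 0.3261)/0.20 = 0.93 SD; (0.5121 - 0.3640)/0.20 = 0.74 SD.
- A1c, BMI, PHQ-9: (0.5000 - 0.3476)/0.20 = 0.76 SD at 0.017.

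These hold the standard error at its 96-per-site value and ignore imputation variance.

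**Does the named comparison reveal the bias?** Assume no true difference and 20% missing per site. Let dropout at one site be logistic in the 6-month change (log odds 0.6 per SD: 29%, 18% and 11% at -1, 0 and +1 SD) and random at the other. Take intention-to-treat as MAR given the 3-month value. Both plausible meanings of per-protocol were tried.

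- *Patients with complete visits.* Intention-to-treat bias is 0.10, 0.09 or 0.06 SD for a 3/6-month correlation of 0.3, 0.5 or 0.7; completers are biased by 0.11 SD. Both err in the same direction. Dropout that depends only on the 3-month value, which is MAR, would also open a gap.
- *Program adherers* (80% adherent, the same adherence/outcome correlation at both sites, 3/6-month correlation 0.5). Intention-to-treat bias is 0.086 SD and per-protocol bias 0.063 to 0.080 SD. The gap of about 0.01 to 0.02 SD is well under its standard error of about √(2/76.8 - 2/96) = 0.07 SD. With no MNAR at all, adherence/outcome correlations that differ by site (0.5 against 0.3, 0.7 against 0.3, or 0.5 against 0) give gaps of 0.07, 0.14 or 0.18 SD.

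Under either meaning, agreement does not rule out MNAR bias and disagreement does not establish it.

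**The case against.** The strongest reply has five parts.

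- *The list is open.* That is true, and the documents do not exclude a better analysis. But one that is not named is not pre-specified and could be chosen after results are known.
- *The paragraph's MNAR example is skipped DKQ questions, not dropout, and it does not mention 6 months.* Also true. The 6-month focus comes from the hypotheses in section 11.2. Item-level non-response is not covered by the calculation above, but comparing two populations does not address it either.
- *Per-protocol is undefined.* Section 8.1 says the study only collects data, and section 3.1 refers to a data collection protocol of four visits, so completers is a fair reading. This limits any statement about adherence, which is why both readings were worked. The conclusion survives under each.
- *The size is conditional.* This stands. It needs departures that differ between sites and the full 20% loss by 6 months, whereas follow-up runs to 12 months. Section 24.2 reports past retention of 80-85%, and visits at convenient locations with a card for each appointment may limit loss. Three-month values absorb part of the bias where they are used.
- *A gap could appear when MNAR is present.* It could, if dropout and adherence are linked. A reader might infer that the comparison can never react to MNAR. That is too strong: it can react, but the reaction cannot be attributed to MNAR or turned into a bound.

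**Conclusion.** The point holds in this form: the one MNAR check that section 13.3 names cannot isolate or bound MNAR bias, its two populations are undefined, and its trigger cannot be settled from observed data. No other section varies the assumption about unseen outcomes.

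Under modest one-site departures (0.25 to 0.5 SD, 20% missing) the size is 0.05 to 0.10 SD of bias, with type I error of 3.4% to 6.2% at 0.025 or 1.8% to 3.6% at 0.0125. If the planned effects were observed, it would take a one-site shift of roughly 0.74 to 1.26 SD, depending on outcome and alpha, to remove significance. The shifts and dropout models are assumptions, not figures from the documents.

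Two stronger readings are not supported. A reader might infer that the primary analysis discards the 3-month data; section 11.2 gives only a power basis, and section 13.3 would allow 3-month scores as imputation covariates, so this is simply not stated. A reader might also infer that the results will be biased; the documents do not show that. What is missing is a means of showing how robust the results are. This should be changed, but it does not undermine the primary estimate.

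**What to change.** In section 13.3, pre-specify a delta-adjusted multiple-imputation analysis of the 6-month site difference for DKQ, PAM-13 and A1c at least:

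1. Define the overall contrast, pooled over the propensity strata, since section 11.1 has the five strata analysed independently.
2. Impute 6-month values by site under MAR with the 3-month value in the model, in the SAS or Stata procedures already named.
3. Shift the imputed values in the unfavourable direction, separately by site, over a range fixed before outcomes are seen, for example 0 to 1.0 SD. The withdrawal tracking described in section 13.3 can inform which shifts are plausible.
4. Report where each conclusion changes, or that it does not change within the range.
5. Run it whatever mechanism is judged to apply.

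The intention-to-treat and per-protocol comparison can stay if wanted, with both populations defined, but should not be labelled an MNAR check.

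The cost is SAP wording and moderate programming, with no new data. The downside is one extra table per outcome and a judgement on the shift range.
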